4.2. FSD201

FSD Pharma Inc. is developing FSD201, an agent that primarily targets medical conditions where inflammation and pain are the major concerns and offers promising hope for the treatment of such conditions. PEA is an endogenous biologically active lipid belonging to the class of *N*-acylethanolamines (NAEs) and exerts anti-inflammatory, analgesic, and neuroprotective properties for the maintenance of homeostasis. PEA is synthesized in the body in response to external stressors and tissue injury. The pleiotropic effects of PEA involve several mechanisms, including activation of the peroxisome proliferator-activated receptor α (PPAR α), the downregulation of mast cell activation of type 1 vanilloid transient receptors (TRPV1) channel, and prevention of NF κ B nuclear translocation among others. PEA also inhibits the release of synthesised mast cell mediators, including histamine and TNF- α .

4.3. Safety and Pharmacokinetic (PK) data from FSD201 Phase I SAD/MAD Study in Healthy Individuals

To evaluate the safety and tolerability of FSD201, a single-center, Phase 1, randomized, double-blind, placebo-controlled, sequential SAD/MAD study with a food-effect arm was conducted.

48 healthy male or female adult light smokers or non-smoker subjects were included in this study. The **primary objective** of the study was to evaluate the safety and tolerability of FSD201 following oral administration of single ascending doses (SAD) ranging from 600 mg to 2400 mg and multiple ascending doses (MAD) ranging from 600 mg to 1200 mg administered twice a day (*b.i.d.*) for seven consecutive days, in healthy subjects. The study's **secondary objectives** were to characterize the pharmacokinetic (PK) profile of FSD201 following single and multiple oral doses in healthy subjects and evaluate the effect of food on the absorption of FSD201. The study schematic is shown in [Figure 1](#).

[figure not shown]

Figure 1 Study Schematic of FSD201 Phase I Clinical Trial.

Absorption of FSD201 increased in a less than dose-proportional manner over the dose range of 600 to 2400 mg following oral administration of single doses of FSD201 in healthy subjects. Administration of FSD201 under fed conditions resulted in a significant increase in PEA absorption rate – for a dose of 1200 mg of FSD201 in a fed state ([Figure 4](#)), it was seen that the

peak plasma concentration was seen to be about 250 ng/mL in about 2 hours as compared to 50 ng/mL in about 45 minutes in fasting state. However, it did not appear to affect the time to reach the peak of concentration of PEA in the high-fat diet, as shown in Figure 4. Peak plasma levels and total exposure during a dosing interval increased in a dose-proportional manner across the dose range 600 to 1200 mg following repeated oral doses. However, the $C_{min ss}$ appeared to increase less than in a dose-proportional manner, as shown in Figure 2.

There appears to be no significant accumulation of FSD201 following repeated doses with 600 and 1200 mg. Following multiple dosing, steady-state was achieved within seven days at the 600 mg dose level and within four days at the 1200 mg *b.i.d.* dose level, as shown in Figure 3.

SAD

[figure not shown]

Figure 2 Mean Plasma Pharmacokinetic Concentrations for FSD201 in the SAD Study (Part A)

MAD

[figure not shown]

Figure 3 Mean Plasma Pharmacokinetic Concentrations for FSD201 in the MAD Study (Part B, Day 1 through Day 7)

Fasted vs Fed

[figure not shown]

Figure 4 Arithmetic Mean Plasma Concentration vs Time Profiles of FSD-201 for single dose of 1200 mg in fed and fasted individuals

Overall, FSD201 following an oral administration of a single dose, ranging from 600 mg to 2400 mg, and multiple doses ranging from 600 mg to 1200 mg *b.i.d.*, were safe and well-tolerated in normal healthy subjects. No serious adverse events (SAEs) were reported for these studies. The safety results seen in this Phase I trial were consistent with published information. There were no Treatment-Emergent Adverse Events (TEAEs) related to clinical laboratory results, ECGs, and physical examination in both the SAD and MAD recipients. No clinically relevant differences were observed between the treatment groups with respect to mean values and changes from baseline for clinical laboratory results, vital signs, and ECG results.

In the SAD study, one vital sign abnormality (hypotension) was experienced by one subject in Cohort 2 [1200 mg], observed during the scheduled measurements, considered a TEAE. This TEAE was considered mild and represented a transient lowering of systolic blood pressure of less than 10 mmHg. Overall, no safety issues were observed for clinical laboratory, vital signs, ECGs, or physical examination results.

4.4. Study Governance

This study is a prospective, randomized, double-blind, placebo-controlled sponsor-initiated trial. The study's design is set to accept individuals who meet the criteria for chronic widespread musculoskeletal nociplastic pain (arising from neurogenic inflammation) secondary to likely “Idiopathic MCAS.” The study will be conducted at three centres: one in Canada and two in the USA. The study will be conducted under an IND (US FDA) and CTA (Health Canada). Participants will be randomized on Day 0 in a ratio of 2:1 to receive 600 mg FSD201 or placebo orally twice daily for 56 days.

4.5. Description of the study population

Adults (≥ 18 years and ≤ 75 years.) with chronic widespread musculoskeletal nociplastic pain (in three or more body regions) likely related to ‘idiopathic MCAS’ are selected and randomized to receive either FSD201 600 mg *b.i.d.* or placebo.

5. Study Objectives

5.1. Main Objectives

- To evaluate the analgesic efficacy of FSD201 compared to placebo in subjects with chronic widespread musculoskeletal nociplastic pain;

5.2. Secondary Objectives

- To evaluate the efficacy of FSD201 as compared to placebo on pain-related function, sleep interference, and global improvement;

- To assess safety and tolerability of FSD201 in subjects with chronic widespread musculoskeletal nociceptive pain;
- To evaluate the change in serum tryptase, IL-6 and IL-1beta serum biomarker levels.

5.3. Study Endpoints

5.3.1. Primary endpoint

Targeted treatment effect of 30% decrease from baseline to Day 28 in the average daily pain intensity score measured by an 11-point numerical pain rating scale (NPRS). Averages will be calculated as follows:

Baseline: calculated weekly average from Day -7 to Day -1

Day 28: calculated weekly average from Day 22 to Day 28

5.3.2. Key Secondary endpoints

Key secondary efficacy endpoints will include changes from baseline to Day 56 as measured by:

- Percentage of subjects achieving $\geq 30\%$ reduction in NPRS score at the end of treatment with FSD201¹
- Change in Patient Global Impression of Change (PGIC) after 56 days treatment
- Change or reduction in patient average daily NPRS after 56 days of treatment¹;
- Change in Patient-Reported Outcomes Measurement Information System (PROMIS) Sleep Disturbance- Short Form (SF) 8a after 56 days treatment
- Change in the PROMIS Pain Interference- SF 8a score after 56 days treatment
- Change in the PROMIS General Life Satisfaction- SF 5a after 56 days treatment
- Change in the PROMIS Fatigue- SF 8a after 56 days treatment
- To determine whether FSD201 treatment reduces serum mast cell tryptase, IL-6 and IL-1beta during treatment.

Key secondary efficacy endpoints will include changes from baseline to Day 28 and Day 56 as measured by:

- Percentage of subjects achieving $\geq 30\%$ reduction in NPRS score¹
- Change in Daily Sleep Interference Scale (DSIS) after 28 and 56 days of treatment¹
- Change in Patient Global Impression of Change (PGIC).

Note:

¹DSIS and NPRS averages will be calculated as follows:

Baseline: calculated weekly average from Day -7 to Day -1

Day 28: calculated weekly average from Day 22 to Day 28

Day 56: calculated weekly average from Day 49 to Day 55 for the NPRS and Day 50 to Day 56 for the DSIS

5.3.3. Other Secondary Endpoints

- Change in pain intensity on the NPRS from baseline to each week of treatment
- Percentage of subjects achieving $\geq 50\%$ reduction in NPRS at Day 56²
- The total amount of rescue medication used.

Note:

²DSIS averages will be calculated as follows:

Baseline: calculated weekly average from Day -7 to Day -1

Day 56: calculated weekly average from Day 49 to Day 55

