6.2. Patient Recruitment

Subjects will be recruited by physician databases.

All subjects will provide written informed consent for the study at the beginning of the Screening Visit, prior to performance of any of the study procedures and collection of study data.

The subject's eligibility for randomization will be determined at Visit 2 according to the inclusion and exclusion criteria set forth in [Section 10.1](#).

A unique identification number will be given to study subjects to keep their information anonymous. Subject numbers will be assigned in sequential order (i.e., the first subject's identification number will be 001, etc.). This number will be used in all CRFs.

Demographic Data and Medical History

The subject's demographic information and medical history will be recorded at the Screening Visit and documented on the appropriate CRF. This will include:

- Demographic information: sex, age, race and ethnicity
- Medical history for the past 10 years prior to screening and other relevant history will be collected, including other types of pain (e.g., arthritis); surgeries; diabetes; cancer; cardiovascular events; and gastrointestinal problems
- Data on MCAS will be captured separately, in detail, including date of onset, and attempted treatments

After providing written informed consent, potential study subjects will be screened for study eligibility during the maximum 17 days screening and baseline period. During this time, subjects will complete daily entries to collect daily pain and sleep disturbance scores, and document rescue medication use (acetaminophen or diphenhydramine). Entries will be collected by means of a Study electronic Application (App) developed for this trial. The app can be installed on the patient's own device (assisted by the study coordinator), or the patient will be provided with a device (phone or tablet) to record these entries daily.

The values recorded on the last seven days before the randomization/Visit 2 will be used to determine the baseline scores. Subjects who completed entries in the App on at least 5 out of 7 days before randomization /Visit 2 and have an average pain intensity between 4.0 and 9.0 that meets the study-specified threshold and who continue to meet all other study eligibility criteria will be enrolled in the study.

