Patients who meet the eligibility criteria will be randomized on Visit 2 in a ratio of 2:1 to receive 600 mg FSD201 or a placebo orally twice daily for 56 days. Subjects will take their first dose of the investigational either FSD201 or placebo in the clinic. An assessment for allergy or hypersensitivity reaction will be conducted immediately after the first dose; signs and symptoms to be evaluated include flushing, skin rash, urticaria, fever, dyspnea, bronchospasm, edema, angioedema, hypotension, and anaphylaxis.

Subjects will continue completing daily App entries throughout the 56 day treatment period including their 11-point pain scale over the last 24 hours, their sleep disturbance score, their rescue medication and their Investigational Compliance.

Subjects will return to the site at Day 14, Day 28 and Day 56/ Early termination visit. A phone call will be made to each subject seven (7) days after the last intake of the investigational product.

Subjects will be monitored for adverse events (AEs) from the date of first dose until the last follow-up visit (AEs noted between signing of Informed Consent Form (ICF) and first dose should be recorded as Medical History). Any SAEs occurring within 7 days after the last investigational medicinal product (IMP) intake will be collected. Efficacy and safety will be assessed as outlined in the schedule of events ([Table 1](#)).

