7.1.7. Withdrawal/Discontinuation Procedures

A subject may be discontinued from the study at the discretion of the Investigator for medical reasons, or if the subject wishes to withdraw. **Subjects who do not meet the additional criteria for entering the Treatment Period at Visit 2 will be discontinued from the study and considered screen fails.** Women who become pregnant during the study and males whose partners become pregnant during the study will immediately be discontinued from the study. Refer to [Section 12.8](#) for Pregnancy report criteria. Subjects may, at the Investigator’s discretion, also be discontinued at any time due to non-adherence to treatment regimen (e.g., <80% of the doses taken, failed urine drug test) and missed visits. If a subject does not return for a scheduled visit, every effort will be made to contact the subject, and document the subject outcome, if possible.

Based on previous studies of PEA and the FSD201 Phase 1 trial, the most likely AEs would be related to gastrointestinal intolerance and/or diarrhea. Based on this, laboratory changes consistent with severe diarrhea including a decrease in kidney function ($\text{eGFR} < 60 \text{ mL/min/1.73m}^2$) or hyperkalemia/hypokalemia (serum potassium $< 3.0 \text{ mmol/L}$ or serum potassium $> 5.5 \text{ mmol/L}$) will cause the patient to be discontinued from treatment. In addition, patients who experience a single SAE probably related to the study drug will also be discontinued (whether or not this SAE is related to gastrointestinal intolerance/diarrhea). Individual stopping criteria are summarized in Table 3.

Stopping Criteria	Value for Stopping
Kidney Function (eGFR)	<60 mL/min/1.73m ²
Potassium	<3.0 mmol/L or >5.5mmol/L
Development of an SAE probably related to the study drug	1 SAE

Table 3 Individual Stopping Criteria

All subjects who withdraw or are discontinued by the Investigator (for any reason) will have an Early Termination Visit performed within 14 (\pm 2) days of discontinuation or withdrawal. If subjects have ongoing AEs at the time of discontinuation, the site should follow up with the patient until all AEs are resolved or closed.

The study will be stopped if there are four individuals with SAEs probably related to the study drug in the FSD201 treatment group. This represents 10% of the expected 40 patients in the FSD treatment group.

8. Treatment Plan

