8.2.1. Rescue Medication

Acetaminophen (maximum daily dose 3,000 mg) or diphenhydramine (maximum daily dose 300 mg) is allowed, starting at the screening visit.

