13.2. Procedures for Expedited Reporting

Responsibility for Reporting Serious Adverse Events to Regulatory Authorities

Ozmosis Research Inc. will provide expedited reports SAEs to Intrinsik for submission to Health Canada and FDA according to applicable guidelines and regulations, i.e. events which are BOTH serious AND unexpected, AND which are thought to be related to protocol treatment (or for which a casual relationship with protocol treatment cannot be ruled out).

Reporting Serious Adverse Events to Local Ethics Boards

Ozmosis Research Inc. will notify all Investigators of all Serious Adverse Events that are reportable to regulatory authorities from this trial or from other clinical trials as reported to the Sponsor. This includes all serious events that are unexpected and related to protocol treatment. Investigators must notify their Research Ethics Board (REB) / Institutional Review Board (IRB) and file the report with their Investigator Site File. Documentation that serious adverse events (SAEs) have been reported to REB/IRB must be kept on file at Ozmosis Research Inc.

Documentation can be any of the following:

- Letter from REB/IRB acknowledging receipt
- Stamp from the REB/IRB, signed and dated by REB/IRB chair, acknowledging receipt
- Letter demonstrating the SAE was sent to the board

All expedited serious adverse events occurring within a centre should also be reported to local REB/IRB.

14. Statistical Methods and Planned Analyses

The intent-to-treat (ITT) population will consist of all randomized subjects. The safety population will include all randomized subjects who receive at least one dose of the study drug. The per-protocol population will consist of all subjects in the ITT population who have no major protocol deviations that would have a significant effect on the efficacy of the study treatment. The ITT

population will be the primary population for all efficacy analyses. All safety data will be summarized based on the safety population. The per-protocol population will be used as the population for sensitivity analyses of the primary and key secondary efficacy endpoints.

All efficacy and safety will be summarized descriptively.

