14.1. Efficacy Analysis

As the primary analysis, the change from baseline in the weekly average of the daily pain intensity measured by NPRS will be analyzed using the mixed model for repeated measure (MMRM) with the treatment as a factor, visit, the interaction between treatment and visit, and baseline as a covariate. The analysis of covariance (ANCOVA) will also be used as an additional analysis. The change in the weekly average of the daily sleep score on Daily Sleep Interference Score (DSIS) and the change in the NPRS score will be analyzed using the same methods for primary endpoint analysis. The percentage of subjects achieving $\geq 30\%$ and $\geq 50\%$ reduction in NPRS score at Day 28 and Day 56 will be analyzed using Fisher's exact test and the logistic regression model. The change in Patient Global Impression of Change (PGIC) and other continuous efficacy endpoints will be analyzed using ANCOVA.

No multiplicity adjustment will be used in this study. The missing data imputation methods and sensitivity analyses for primary and key secondary efficacy endpoints will be included in Statistical Analysis Plan (SAP).

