14.4. Methods for Handling Missing Data

Reasonable efforts will be made to obtain complete data for all subjects; however, missing observations may occur due to subjects lost to follow-up or non-adherence to required assessments. The reasons for missing data will be evaluated. In addition, the distribution of prognostic factors between subjects with data and those without data will be examined to evaluate any potential sources of bias. In the absence of any apparent systematic loss, data will be analyzed assuming that these observations are missing at random.

For efficacy endpoints, missing data will be adjusted in the analysis by using the method of last observation carried forward (LOCF). A sensitivity analysis will be carried out using the baseline observation carried forward (BOCF).

15. Investigational Obligations

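### The rescue-medication endpoint is stated only as a total, with no window, scaling for recorded days, rule for the two drugs or rule for unrecorded days

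*Combined protocol and SAP*

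**What the plan says.** Section 5.3.3 (Other Secondary Endpoints) gives the whole definition as "The total amount of rescue medication used", and the synopsis uses the same words. By contrast, Sections 5.3.1 and 5.3.2 give the pain and sleep scores explicit averaging windows. The note under Section 5.3.3 deals only with averages of the sleep interference scale.

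Section 8.2.1 names two rescue drugs: "Acetaminophen (maximum daily dose 3,000 mg) or diphenhydramine (maximum daily dose 300 mg) is allowed, starting at the screening visit". Section 6.2 treats them as one diary item, asking subjects to "document rescue medication use (acetaminophen or diphenhydramine") from screening onward, and then states "Subjects will continue completing daily App entries throughout the 56 day treatment period". Section 6.1 allows up to 17 days of screening.

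Subjects who stop early "will have an Early Termination Visit performed within 14" (±2) days, under Section 7.1.7. No continued diary is described for them. Section 14 states "The intent-to-treat (ITT) population will consist of all randomized subjects" and makes this the primary population for efficacy.

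Section 14.1 does not name rescue use. The nearest provision is that "other continuous efficacy endpoints will be analyzed using ANCOVA". Its deferral of missing-data methods to the SAP covers primary and key secondary endpoints, and rescue use is neither. Section 14.4 gives a general rule: "For efficacy endpoints, missing data will be adjusted in the analysis by using the method of last observation carried forward (LOCF"), with baseline observation carried forward as a sensitivity analysis.

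**The concern.** A total grows with the number of days on which use is recorded, so it mixes how much rescue a subject took with how long the subject was observed. All randomized subjects are analysed and diaries appear to end with participation, so early leavers contribute short records. If one arm loses more subjects, its total falls for that reason alone.

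The two drugs raise a separate question. Their daily caps differ by a factor of ten, and nothing says whether a total is formed within each drug or across both.

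Rescue is allowed throughout, and the pain analysis in Section 14.1 makes no stated allowance for it. This is the only endpoint that measures rescue use, so it is where a reader will look to see whether similar pain scores were reached with similar rescue. A measure that depends on exposure answers that question poorly.

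**Working it through.** The documents give no planned figure for this endpoint, so there is none to reproduce. The inputs they do give are 56 treatment days, up to 17 screening days, and caps of 3,000 and 300 mg/day. Dropout, diary-gap and daily-use values below are assumptions, shown as ranges where they drive the result.

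**1. Early stopping.** Recorded total = daily use × recorded days. Assume a constant 1,000 mg/day of acetaminophen.

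| Recorded days | Total | Share of completer's total | Mean per recorded day |
|---|---|---|---|
| 14 | 14 g | 14/56 = 25% | 1,000 mg |
| 28 | 28 g | 28/56 = 50% | 1,000 mg |
| 42 | 42 g | 42/56 = 75% | 1,000 mg |
| 56 | 56 g | 100% | 1,000 mg |

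**2. Diary gaps.** If 10%, 20% or 30% of days are unrecorded and count as zero, the total is 90%, 80% or 70% of true use.

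**3. Between arms.** Assume equal true daily use, use unrelated to dropout, and dropout proportion d spread evenly over 56 days. Mean recorded days = 56 × (1 − d/2).

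- d = 10%: 53.2 days
- d = 20%: 50.4 days, and 50.4/53.2 − 1 = −5.3%
- d = 30%: 47.6 days, and 47.6/53.2 − 1 = −10.5%

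Under the same assumptions, the order of the arms reverses only if the arm with more dropout truly uses more by less than 53.2/50.4 − 1 = 5.6%, or 53.2/47.6 − 1 = 11.8%.

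**4. The carry-forward rule.** Applied to the running total, it freezes the total at its last value, so the 25%, 50% and 75% in step 1 stand. Applied to daily use, it fills the remaining days and gives 56 g in every row, but only because use was assumed constant. Section 14.4 does not say which is meant.

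**5. Window.** Rescue is recorded from screening, so a total without a stated window could cover 56 days or up to 56 + 17 = 73 days.

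**6. Two drugs.** Ratio of caps: 3,000/300 = 10. If milligrams were summed with both drugs at cap, diphenhydramine would be 300/3,300 = 9.1% of the sum. Over 56 days, diphenhydramine at its cap totals 0.3 × 56 = 16.8 g, while acetaminophen at one third of its cap totals 1 × 56 = 56 g.

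**The case against.** A reader might infer that the plan adds milligrams of the two drugs. The text neither orders nor excludes this, and a total for each drug fits the words equally well. Step 6 is therefore conditional on a rule that nobody has written, and the factor of ten compares daily maxima, not actual use.

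A reader might also infer that early leavers and subjects who miss diary days will certainly score as low users. The documents do not support that. Section 14.4 has a carry-forward rule that, applied to daily use, would fill the gap in the constant-use case. No section says that an unrecorded day counts as zero, and the schedule of events lists rescue recording at the Early Termination visit. These points remove the certainty but not the ambiguity, because the level at which the rule operates is unstated and nothing says that the visit recovers later days.

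A third tempting reading is that the endpoint will point the wrong way. That depends on dropout rates that the documents do not give, and under the assumed rates the distortion is modest. Nor is this the only source of information on rescue, since concomitant medication is recorded at the visits and summarized descriptively (Section 14.3).

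Finally, the endpoint is minor. It plays no part in the responder-based Go/No-Go calculation in Section 10.5. That stands, and it limits the weight of the point.

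**Conclusion.** The point holds as a gap in definition. The endpoint lacks a window, scaling for recorded days, a rule for the two drugs and a rule for unrecorded days, and neither Section 14.4 nor the deferral to the SAP supplies them.

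Taken literally, the total understates use in subjects with shorter records: 25% to 75% of a completer's total for stops between Day 14 and Day 42 at constant use. At arm level the shortfall is about 5% to 10% for 20% to 30% against 10% dropout. It falls on whichever arm loses more subjects. The arm-level figures assume evenly spread dropout unrelated to use. If heavier users leave earlier, the shortfall would be larger.

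The change is worth making but not essential. The primary analysis and the sample size do not depend on it.

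**What to change.** In Section 5.3.3, the synopsis and the SAP, replace the total with the following, for each drug separately:

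- mean daily use (mg/day) over treatment-period days with a diary entry, for Days 1–28 and Days 1–56;
- the percentage of those diary days with any rescue use.

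Compare the arms with adjustment for use in the baseline week, when the App already records rescue. State that unrecorded days are left out and not counted as zero, and that last observation carried forward is not applied to a running total. In the example of step 1, the new measure gives 1,000 mg/day whether 14 or 56 days are recorded.

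The cost is protocol and SAP wording and a few more summaries for a minor endpoint. Two limits remain. The measure is still biased if subjects leave or skip entries because their pain is poorly controlled. It also needs the App to capture drug and dose for each day. The documents say that rescue use is recorded daily but not in that detail, so this should be confirmed first.
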